7.8 Trial Closure

The trial will be declared closed when either i) the last surviving patient either dies or ii) is withdrawn from the trial, or iii) six months after the last patient has been recruited into the study or iv) the Sponsor decides to terminate the study, whichever occurs first.

7.9 Carry-over Protocol

If, at the time of trial closure, there are sufficient patients still deriving clinical benefit (in the opinion of the relevant investigators) from DTP3 therapy, the Sponsor may roll them over into an extension protocol, although the decision to do this will be at the sole discretion of the Sponsor.

8. STATISTICS AND DATA ANALYSIS

Prior to the analysis of the final study data, a detailed Statistical Analysis Plan (SAP) will be written and approved describing all analyses that will be performed. The SAP will contain any modifications to the analysis plan described in this section and should be considered the definitive point of reference for all statistical analyses.

Appropriate descriptive methods will be used to summarise the data obtained in this study. Continuous variables will be presented by descriptive statistics including the number of observations, arithmetic mean, standard deviation, minimum, median and maximum. Categorical variables will be summarised by frequency and percentage.

8.1 Justification for sample size

Dose Escalation

The performance of the proposed two-stage CRM was assessed by simulations. Initial simulations gave a good performance for determining the correct MTD at least 55% of the time for up to 24 patients under seven clinically relevant scenarios (more details can be found in the Statistical Simulation Plan). Most patients are dosed at the recommended MTD. If all doses are too toxic, the design will correctly stop 60% of the time.

Dose Expansion

It is estimated that 24 patients per indication [MM and DLBCL] in the expansion phase produces a onesided 90% lower-limit confidence interval of at least 27.7% when the observed response rate is \geq 41.7% using the Exact Clopper-Pearson interval method. This exceeds the minimum response rate of 25% required to justify further testing for each cohort.

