1.4 Justification of the DTP3 starting dose

For the purpose of deriving the original human starting dose for the clinical trial, the rat was considered the most sensitive species. This is based on the observation that, although low, protein binding is approximately 80% in the rat, compared to approximately 20% in man, and therefore reference to the rat NOAEL derives the most conservative human starting dose.

Allometrically scaled (*i.e.* divided by 6) the NOAEL in the rat of 100 mg/kg is a human dose equivalent of 16 mg/kg. This human dose equivalent was reduced by a factor of 4 to correct for the difference in protein binding to derive a dose of 4 mg/kg. A further safety factor (approximately 8) was applied to establish the human starting dose of 0.5 mg/kg.

The pharmacokinetic profile of DTP3 was assessed using the pooled pre-clinical data available from the mouse, rat and dog studies undertaken to date and selected pre-clinical datasets were then subjected to simple scaling methodology to predict the potential clearance of the compound in man. Based upon the lower of the two human clearance predictions (derived from the rat), the AUC $_{0.48}$ in man at the proposed clinical starting dose of 0.5 mg/kg, would be expected to be approximately 2300 ng.h/ml, i.e. between 12 and 31% of the unbound AUC achieved over a 48 h period following daily dosing to the dog and rat at the lowest dose levels used in the one month studies (10 and 8% if based on total concentrations).

The projected human exposure of 2300 ng.hr/mL at the original starting dose of 0.5 mg/kg compares to the exposure of 1029 ng.hr/mL at a minimally effective dose of 2.5 mg/kg in the mouse MM xenograft model. At the highest proposed clinical dose of 20 mg/kg, assuming dose proportionality, the AUC $_{0.48}$ in man would be expected to be approximately 92600 ng.h/ml *i.e.* between 59 and 225% of the unbound AUC achieved over a 48 h period in dog and rat at the highest-dose level in the two one month toxicology studies (50 and 55% if based on total concentrations).

Additionally, potential safety risks will be substantially mitigated as DTP3 will be administered i.v. 3 times per week by a 1 hr infusion compared to the pivotal toxicity studies, in which DTP3 was administered daily by a fast 10 min infusion. The maximum DTP3 plasma concentrations will therefore be significantly reduced, and the infusion may be terminated prematurely if this is considered necessary.

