3. STUDY DESIGN

This is a multi-centre Phase I/IIa dose escalation and subsequent cohort expansion study. Up to 37 DLT evaluable patients with multiple myeloma or diffuse large B-cell lymphoma will be entered into an initial dose escalation stage. A DLT evaluable, patient must have received at least 10 of the 12 scheduled Cycle 1 doses of DTP3 (unless a DLT prevented further DTP3 dosing). Subsequently at least 24 response evaluable-patients with multiple myeloma and at least 24 response evaluable patients with diffuse large B-cell lymphoma will be entered into an open label dose expansion stage. A response evaluable patient is defined as one who has completed at least one response assessment after at least two cycles of DTP3, unless disease progression has been documented at earlier time point.

During the dose escalation stage, non-DLT evaluable patients will be replaced.

During the dose expansion stage, non-response evaluable patients may be replaced after discussion with the medical monitor.

It will take a maximum of 32 months to conduct the dose escalation stage of the trial which will lead to a RP2D, and a further 20 months to complete the dose expansion phase.

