5.1 Dose Escalation Stage

Patients will be administered DTP3 intravenously (i.v.), given as a one hr infusion three times per week (with an inter-dose interval of a minimum of 40 hr and a maximum of 72 hr) in continual 4-week cycles until disease progression or unacceptable toxicity, whichever occurs first.

In the dose escalation stage, the following maximum potential range of DTP3 dose levels will be examined:

2.0, 4.0, 6.0, 9.0, 12.0, 16.0, 20.0, 30.0, 45.0, 67.0, 98.0 mg/kg

The dose escalation will employ a flexible Bayesian Continuous Reassessment Methodology (CRM) to obtain the Maximum Tolerated Dose (MTD) of DTP3 associated with a target Dose Limiting Toxicity (DLT) of 30% from a range of up to 11 doses.

A TDSMC (Section 5.4) will review, on an ongoing basis, all available safety and efficacy/PD/PK data.

For the proposed design, the first patient will be given a starting dose of 2.0 mg/kg. If no DLT occurs, the next patient will only be dosed at the next higher dose after the preceding patient has completed 4 weeks of treatment.

The TDSMC may recommend increasing the number of patients at specific tolerable doses, to obtain further information to aid dose selection or evaluation of doses which are intermediate to the prespecified dose levels in order to further characterise the relationship between dose level and emergent toxicities.

If a DLT is observed at any dose level, dose escalation will revert to 3 patients per cohort (including the cohort with the initial DLT) to further assess the observed safety data. Once a DLT has been observed, the CRM model will commence estimating the DLT rate at each dose level and recommend the next best dose level with an estimated DLT rate closest to 30% for subsequent patients, using all the accrued DLT data at all doses. An empiric dose-toxicity model $F(\chi,\beta)=\chi^{A}exp(\beta)$, $0<\chi<1$ will be used, where the slope parameter β is assumed to follow a normal distribution with prior mean 0 and a pre-specified prior variance of 1.

The first patient in each cohort will not be enrolled until all patients at the immediately lower cohort have completed the DLT monitoring period and the TDSMC has reviewed the safety data to decide whether to proceed to the next dose level.

The CRM will continually re-estimate the MTD using all accrued DLT data during both the dose escalation and dose expansion stages.

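### Section 8.1 claims a 60% chance of stopping if all doses are too toxic, but the written CRM rules contain no toxicity stop, and performance is quoted for 24 patients against a cap of 37

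*Protocol*

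**What the plan says.** Protocol section 8.1 justifies the dose-escalation size by simulation of a two-stage CRM. It reports good performance for "determining the correct MTD at least 55% of the time for up to 24 patients under seven clinically relevant scenarios", adds that "Most patients are dosed at the recommended MTD", and ends: "If all doses are too toxic, the design will correctly stop 60% of the time". It refers to a Statistical Simulation Plan for details.

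Section 5.1 gives the working rule. One patient is treated per level until the first DLT, and cohorts are of 3 after that. From then on the model is to "recommend the next best dose level with an estimated DLT rate closest to 30% for subsequent patients", using a one-parameter empiric model with a normal prior (mean 0, variance 1), a 30% target and up to 11 levels. The Study Summary repeats this rule. Section 8.3 defines the MTD in the same way, as the dose whose estimated DLT rate is nearest the 30% target.

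On size, section 3 states: "Up to 37 DLT evaluable patients with multiple myeloma or diffuse large B-cell lymphoma will be entered into an initial dose escalation stage". The Study Summary and section 5 give the same cap.

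**The concern.** A design can stop for toxicity with some probability only if it has a condition under which it stops. Neither the CRM rule nor the MTD definition has one, and neither allows the result that no level is acceptable. Section 8.1 therefore credits the design with a property that its written rules lack.

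An ethics committee or regulator reading section 8.1 would take 60% as a quantified safeguard against a dose range that is toxic throughout. Under the rules as printed, the model would go on recommending a level in that situation and would name an MTD at the end.

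The patient number is a second mismatch in the same paragraph. The simulations are described as initial and run to 24 patients, the escalation stage allows 37, and nothing in section 8.1 supports 37.

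**Working it through.** **Step 1. The plan's 60% under the written rule.** Write p̂ⱼ for the estimated DLT rate at level j under the model xⱼ^exp(β), β ~ N(0,1). The rule in sections 5.1 and 8.3 is

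d* = the level j (1 to 11) that minimises |p̂ⱼ − 0.30|.

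A smallest value among 11 numbers always exists, so d* always exists. The model's estimates rise with dose. If the lowest level is estimated at 0.50, its distance is 0.50 − 0.30 = 0.20, every higher level is further away, and the lowest level is recommended. The stopping probability of the algorithm is therefore 0% for any skeleton, any true toxicity curve and any cap. The stated 60% does not reproduce.

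**Step 2. What the written rule does when all levels are too toxic.** Monte Carlo, 600 trials per setting; the standard error near 60% is √(0.6 × 0.4 / 600) = 2 percentage points.

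- From the protocol: 11 levels, target 0.30, prior N(0,1), single patients to the first DLT, then cohorts of 3.
- Assumed, because the protocol does not give them: indifference-interval skeletons with half-width 0.04, 0.05 or 0.07 and prior MTD at level 6; no upward skipping; logistic true curves (slope 0.5 per level when all levels are toxic, 0.7 otherwise); true DLT rate at the lowest level 0.40, 0.50 or 0.60.

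Result: 0% of trials stopped. The lowest level was named MTD in 85–100% of trials at 24 patients and 94–100% at 37.

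**Step 3. What would give about 60%.** An assumed rule was added: stop if P(DLT rate at the lowest level > 0.30) exceeds a cutoff. Percentage of trials stopped, for two of the three skeletons:

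| Half-width | True rate, lowest level | Cutoff | 24 patients | 37 patients |
|---|---|---|---|---|
| any | any | no rule (as written) | 0 | 0 |
| 0.04 | 0.40 | 0.95 | 28 | 43 |
| 0.04 | 0.40 | 0.90 | 47 | 60 |
| 0.04 | 0.40 | 0.80 | 63 | 78 |
| 0.04 | 0.50 | 0.95 | 64 | 83 |
| 0.07 | 0.40 | 0.95 | 17 | 28 |
| 0.07 | 0.40 | 0.80 | 43 | 61 |
| 0.07 | 0.50 | 0.90 | 64 | 83 |
| 0.04 | 0.60 | 0.80 | 98 | 100 |

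Across all settings and cutoffs (0.70 to 0.95) the range was 17% to about 100% at 24 patients and 28% to 100% at 37. A figure near 60% can come from several combinations of rule, scenario and cap, so it cannot be traced back to one of them.

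**Step 4. The cap of 24 against 37.** With true MTDs at levels 2, 4, 6, 8 and 10 and no stopping rule, correct selection was 42–57% at 24 patients and 53–68% at 37. The stated minimum of 55% cannot be checked exactly, because the skeleton and the seven scenarios are not in the protocol. The direction is clear: under these assumptions selection improves with the larger cap.

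**The case against.** Four replies deserve weight.

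- **The rule may exist elsewhere.** Section 8.1 points to the Statistical Simulation Plan, which is not at hand. A conventional posterior-probability rule can give a stopping rate near 60%, so the likeliest explanation is a simulated rule that was never carried into the protocol. That stands as an explanation, but it does not cure the text. A toxicity stop governs conduct during escalation, and section 8 places the SAP before the final analysis, so the rule cannot be left to the SAP.
- **The trial can be halted by people.** The TDSMC decides before each next level (5.1), recommends whether to escalate (5.4), endorses the CRM output (10.2) and can judge any other toxicity a DLT (5.1.1). The sponsor can terminate (7.8). The RP2D is a committee decision, and section 8.3 requires the estimated DLT rate with a 90% interval, which would expose a toxic MTD. All of this stands. A reader might infer that the trial has no protection against a toxic range; the protocol does not support that. But none of these routes has a threshold, so none can be the source of a simulated 60%.
- **The larger cap helps.** That stands for correct selection: 55% at 24 patients is probably conservative for 37.
- **The other figures are not refuted.** A reader might infer that the allocation statement, "Most patients are dosed at the recommended MTD", is implausible. It concerns the recommended dose, which is not the same as the true MTD, and any recalculation depends on an assumed skeleton and assumed curves. It is unverified, not disproved.

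A reader might also take the words "At the highest proposed clinical dose of 20 mg/kg" in section 1.4 as evidence that the simulations covered only seven levels. That sentence belongs to the argument for the 0.5 mg/kg starting dose of the earlier trial, and section 8.1 does not say how many levels were simulated.

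**Conclusion.** The point holds in a limited form. Section 8.1 states a 60% stopping probability for a toxic dose range, while the algorithm in sections 5.1 and 8.3 stops 0% of the time. The 0% needs no simulation assumption; it follows from a rule that always selects the nearest level. That the lowest level would usually be named MTD (85–100% of trials at 24 patients, 94–100% at 37) does rest on the assumed skeletons, curves and lowest-level rates of 0.40 to 0.60, and it describes the algorithm without committee intervention.

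The mismatch of 24 and 37 patients is real but less serious. It probably leaves the 55% on the safe side. It does mean that no stated operating characteristic belongs to the current cap, and that any stopping rate would change with it: 63% at 24 patients became 78% at 37 under one assumed rule.

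The documents do not establish that the figures come from a different design.

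**What to change.** Reconcile sections 5.1, 8.1 and 8.3 and the matching text of the Study Summary in one of two ways:

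- state in section 5.1 the toxicity stopping rule that the simulations used, and allow in section 8.3 for the outcome that no MTD is declared; or
- delete the 60% sentence from section 8.1.

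The content of the rule is for the sponsor to set.

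In either case, re-run the simulations for the current design (11 levels, up to 37 DLT-evaluable patients, single-patient run-in, then cohorts of 3, with the skeleton and prior actually in use). Report correct selection, allocation and stopping rates from that run in section 8.1 in place of the present figures.

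The cost is some simulation work and amendment wording. The restated figures may be less favourable than those now printed.

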8.2 Analysis Sets

Three study populations will be defined:

- Three study analysis sets will be defined:
- **The safety analysis set** will be used as the analysis population for all safety endpoints and comprises all patients who receive at least one dose of DTP3.
- **The efficacy analysis set** will include all patients who receive at least one dose of DTP3 and will be used as the analysis population for efficacy endpoints.
- **The per protocol analysis set** will be used as a sensitivity analysis for efficacy and pharmacodynamic endpoints and comprises patients who:

- The **per protocol analysis set** will be used as a sensitivity analysis for efficacy and pharmacodynamic endpoints and comprises patients who:
 - Fulfil all the inclusion and none of the exclusion criteria
 - Received at least 2 cycles of DTP3 (*i.e.* ≥8 weeks of therapy) or have documented progression at an earlier time point.
- Have at least one efficacy assessment undertaken after ≥8 weeks of therapy or have documented progression at an earlier time point.
- Have completed PD blood and bone marrow (MM) /tumour (DLBCL) sampling (after seventh dose of DTP3)

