Whilst the majority of patients with DLBCL can effectively be cured with front-line immunochemotherapy regimens [largely consisting of anthracycline combination chemotherapy and an anti-CD20 antibody] over a third will either be refractory to therapy or relapse after an initial response.^{22,23,24} The prognosis in this population remains poor, with typical reinduction regimens consisting of combination chemotherapy (plus/minus rituximab) consolidated with autologous stem cell transplant (in selected cases) antibody drug conjugates and bispecific antibodies.^{25,26,27,28}

A minority of relapsed/refractory patients are suitable for treatment with anti-CD19 CAR T-cell regimens. Although a small proportion of these may derive long term disease remission (potentially consistent with a curative outcome) most patients experience either no response or short-lived remissions.^{29,30,31}

The outcome for patients failing to respond to an initial salvage regimen is poor, with a median overall survival of about 6 months.^{33,34,35,36} Likewise for those patients who are not suitable for intensive reinduction therapies there is an urgent need to improve outcomes.

Overall, therefore, the relapsed/refractory MM and DLBCL settings of the current study represent major unmet medical challenges in desperate need of novel therapeutic strategies capable of achieving durable responses in patient populations devoid of standard of care management regimens.

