5. TREATMENT

This is a multi-centre Phase I/IIa dose escalation and subsequent cohort expansion study. Up to 37 DLT evaluable patients with MM or DLBCL will be entered into an initial dose escalation stage. A DLT evaluable, patient must have received at least 10 of the 12 scheduled Cycle 1 doses of DTP3 (unless a DLT prevented further DTP3 dosing). Subsequently at least 24 response evaluable patients with MM and at least 24 response evaluable patients with diffuse large B-cell lymphoma will be entered into an open label expansion stage. A response evaluable patient is defined as one who has completed at least one response assessment after at least two cycles of DTP3 or has documented disease progression at an earlier time point.

In both stages, DTP3 will be administered as a one-hour infusion three times per week (with an interdose interval of 40 h to 72 h, with a larger interval due to non medical reasons if approved by the medical monitor).

The patient's most recently available weight should be used when calculating the amount of DTP3 to administer (see Pharmacy Manual for details of how to calculate the amount of DTP3 to be used). The weight used to calculate the dose of DTP3 can have been taken up to 10 days prior to administration of the first dose of each cycle.

Treatment for any individual patient will comprise continuous four-week cycles until disease progression (as defined in Appendices A and B), unacceptable (drug related) toxicity, or study termination, whichever occurs first.

Should a patient achieve a CR (DLBCL) or \geq PR (MM) of at least 12 weeks duration, the TDSMC will review all available data for that patient (AEs, clinical efficacy, PK, PD, DTP3 dose intensity) and make a recommendation to the relevant investigator about whether to reduce the frequency of DTP3 administration.

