7.2 Safety Assessments (Expansion Stage)

7.2.1 Laboratory safety analysis

Haematology, biochemistry and urinalysis will be performed WEEKLY in Cycle 1 of treatment (within a 72 hour time frame, up to 3 days prior to infusion), EVERY OTHER WEEK during Cycle 2, and then 4-WEEKLY thereafter from Cycle 3 onwards. Testing can be performed within a 72-hour time frame before the next scheduled Day 1 of dosing),

Coagulation (aPTT, PT) will be assessed 4-WEEKLY.

Serum pregnancy test (where appropriate) at beginning of each cycle of DTP3 and then monthly for six months after cessation of DTP3 therapy.

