7.4 Pharmacodynamics

Mandatory samples (unless technically not possible) for pharmacodynamic (PD) assessment will be taken as follows:

- At screening (within 28 days prior to DTP3 treatment)
- **24 hours** (range 18-36 hr) after the **fourth dose** of DTP3 treatment (Cycle 1, Week 2, Day 2)

Tissue will be collected as follows on each occasion for PD, genetic and biomarker assessment and sent in their entirety to the Hammersmith site ([name] lab):

- MM: 50 mL of blood and 10 mL of bone marrow aspirate
- DLBCL: 50mL of blood and a tumour biopsy (18G core), if accessible.

7.5 *Efficacy* Assessments

7.5.1 MM

Routine efficacy assessments will be performed every 4 WEEKS (see Trial Assessment Schedule, Appendix C) unless clinically indicated at an earlier time point. The following assessments will be performed on a 4-weekly basis:

- Serum protein electrophoresis and paraprotein quantification
- Serum free light chain
- 24h urine collection electrophoresis (only in patients with detectable urinary M protein at screening)
- Biochemistry panel
- Full Blood Count

The necessity for bone marrow aspirate and biopsy and/or radiological imaging will be determined by the patient's individual clinical course and will only be undertaken when judged appropriate by the investigator for determination of response or progression, as follows:

If a complete (or stringent complete) response is suspected:

Two independent measurements (according to normal institutional practice) are required to confirm:

- negative immunofixation: serum
- negative immunofixation: urine

If these two independent measurements are consistent with the definition of a complete response, then a bone marrow aspirate and biopsy should be performed

If progression is suspected:

This can be determined by measurement of any relevant disease parameter, including radiological imaging and/or bone marrow plasma cell percentage, but should be confirmed by two independent measurements, according to normal institutional practice.

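### The per-protocol and response-evaluable definitions keep an early failure only if progression is documented, so some deaths before week 8 leave the efficacy sensitivity analysis and the count of 24

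*Protocol*

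**What the plan says.** Protocol Section 8.2 defines two sets that matter for response. The efficacy analysis set is everyone who received DTP3 at least once, and it serves the efficacy endpoints. The per-protocol set is a sensitivity analysis for efficacy and pharmacodynamics. Besides eligibility, it asks for two cycles (glossed as eight weeks or more), for patients to "Have at least one efficacy assessment undertaken after ≥8 weeks of therapy or have documented progression at an earlier time point", and for completed PD sampling, placed there after the seventh dose. Earlier progression is the only exception to the two-cycle and assessment conditions; the PD-sampling condition has none.

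The response-evaluable definition (synopsis and Sections 3, 5 and 5.2) works the same way. It needs a response assessment after two cycles, with one alternative: "or has documented disease progression at an earlier time point" (Section 3 words this slightly differently). The target of at least 24 per cohort is counted on these patients.

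Section 5.5 bars replacement after withdrawal for progression or unacceptable toxicity. Other non-evaluable patients may be replaced once the medical monitor has been consulted. Death is not named.

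For myeloma, "Routine efficacy assessments will be performed every 4 WEEKS" (Section 7.5.1). DLBCL imaging is 8-weekly (Section 7.5.2). Section 8.1 justifies the sample size by a one-sided 90% lower limit of 27.7% at an observed rate of at least "41.7% using the Exact Clopper-Pearson interval method", and adds: "This exceeds the minimum response rate of 25% required to justify further testing for each cohort".

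**The concern.** Two early outcomes are informative about response but are not admitted.

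- **Death before week 8 without documented progression.** This is a treatment failure. The response criteria in Appendices A and B do not list death as progression, so the exception does not cover it. The patient leaves the sensitivity set, is not counted toward the 24, and may be replaced. A DLBCL patient can die before the first scheduled scan.
- **A documented myeloma response before week 8, followed by stopping treatment without progression.** With 4-weekly testing such a response can be seen, yet the patient is dropped. This lowers the sensitivity ORR.

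Membership of the set therefore depends on outcome. A sensitivity analysis should test the primary result, but this one removes some failures and some responders by definition, so agreement with the primary tells the reader little. The evaluable definition also decides when a cohort has reached its 24 and who may be replaced, so the effect reaches recruitment as well as a secondary table.

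**Working it through.** **Inputs from the protocol.** 24 per cohort, 41.7% observed (10/24), one-sided 90% exact limit, 25% minimum (Section 8.1). Median overall survival is about 10 months in myeloma, and in DLBCL after a failed salvage regimen the protocol describes patients "with a median overall survival of about 6 months" (Section 1.1).

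**Assumed input.** d is the share of treated patients dying before week 8 without documented progression. The documents give no figure; 5%, 10% and 20% are shown.

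**Step 1: reproduce the plan's figure.** The one-sided 90% Clopper-Pearson lower limit for x responders among n is the 10th percentile of a Beta(x, n − x + 1) distribution. For 10/24 it is 27.72%, matching the stated 27.7%.

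**Step 2: no replacement, 24 treated.** With 9 responders, 9/24 = 37.5% and the limit is 24.06%, below 25%. Remove one early death: 9/23 = 39.1%, limit 25.18%, above 25%. One patient changes the reading.

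**Step 3: replacement up to 24 evaluable, 10 responders.** Adding early deaths back as non-responders:

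- none: 10/24, limit 27.7%
- one: 10/25, limit 26.5%
- two: 10/26, limit 25.4%
- three: 10/27, limit 24.4%

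Here it takes three excluded deaths to cross the bar.

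**Step 4: error rates when the true all-treated ORR is 25%.** If all excluded patients are non-responders, the response probability among those kept is p = 0.25/(1 − d). For a replaced cohort the chance of a pass is P(X ≥ 10) with X ~ Binomial(24, p). Without replacement, the number excluded is Binomial(24, d), and the event is that the reduced set has a limit above 25% while the 24 treated have fewer than 10 responders.

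| d | p among those kept | P(at least 10/24), replaced cohort | P(reduced set passes, treated set fails), no replacement |
|---|---|---|---|
| 0 | 25.0% | 5.5% | – |
| 5% | 26.3% | 7.4% | 4.3% |
| 10% | 27.8% | 10.1% | 6.5% |
| 20% | 31.3% | 18.8% | 12.4% |

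**Step 5: scale for d.** Under exponential survival with median m months, the share dead by week 8 (56/30.4375 = 1.84 months) is 1 − 2^(−1.84/m). This is 12% for m = 10 and 19% for m = 6, or 2.9 and 4.6 of 24. These are deaths from any cause. Only those without documented progression are excluded, so d should be smaller, and the 20% row is best read as an outer bound.

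**The case against.** The strongest reply is that the primary analysis already handles this. All treated patients form the efficacy set, replacing a patient does not remove that patient from it, and nothing in the protocol applies the 25% bar to the per-protocol set. A minimum-exposure per-protocol set beside an all-treated primary is conventional, and Section 8 lets the SAP, which is not shown, modify the plan. All of this stands. It limits the point to the sensitivity analysis, the counting of the 24 and replacement.

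A reader might infer more than the documents support:

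- **That the sensitivity ORR is conditioned on surviving eight weeks.** It is not. A patient who progresses and then dies early is kept.
- **That the sensitivity ORR will usually look better.** The direction is not settled, because losing early myeloma responders pulls the other way.
- **That all early deaths lack documented progression.** Nothing supports this. Assessments can be brought forward when clinically indicated (Sections 7.5.1 and 7.5.2), and Section 1.1 gives a myeloma median PFS of about 5 months against 10 for survival, so progression will often come first. The 6-month DLBCL figure also describes patients failing an initial salvage regimen, not exactly this trial's population.
- **That the bar would be crossed in either cohort.** If half of the 12% early myeloma deaths were excluded, 24/(1 − 0.06) is about 26 treated, and 10/26 still passes at 25.4%.
- **That the 72-hour sampling allowance makes the scheduled week 8 test too early.** In Section 7.2.1, "Testing can be performed within a 72-hour time frame before the next scheduled Day 1 of dosing" concerns safety laboratory tests. Section 7.1.1 gives a 72-hour limit for myeloma tests in escalation only. One qualifying assessment suffices, so a patient who continues qualifies at the next.

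**Conclusion.** The point holds in limited form. As written, an early death without documented progression drops out of the efficacy sensitivity analysis, does not count toward the 24, and is open to replacement; an early responder who stops before week 8 drops out too. The primary ORR is sound.

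The effect can be material at this sample size: one excluded death separates 24.1% from 25.2% when there are 9 responders among 24 treated. In a replaced cohort with a true all-treated ORR of 25%, the chance of reaching 10/24 moves from 5.5% to between 7.4% and 18.8% for d from 5% to 20%. These rates rest on the assumed d and on every excluded patient being a non-responder; excluded early responders would reduce them.

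**What to change.** - In Section 8.2, in both the two-cycle and the assessment conditions, and in every response-evaluable definition (synopsis, Sections 3, 5 and 5.2), replace the single exception with: *documented progression, documented response, or death from any cause at an earlier time point*.
- State that early deaths without a documented response count as non-responders.
- In Section 5.5, add death to the reasons for which a patient is not replaced.
- Do not apply the PD-sampling condition to the efficacy sensitivity set; keep it for the pharmacodynamic analysis. Otherwise a patient who dies before that sample would still be excluded after the rewording.

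The cost is wording only, with no new visits or procedures. The sensitivity ORR may come out slightly less favourable.
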